## 16. SAFETY MEASUREMENTS AND PARAMETERS

### 16.1. Safety measurements

All patients who have received at least one dose of study medication will be considered the Analysis Population and will be evaluated for toxicity from the time of their first drug administration. When toxicity occurs, it should be graded according to the NCI Common Toxicity Criteria, version 5.0.

### 16.2. Safety parameters

#### Adverse Events (AE)

An adverse event (AE) is any untoward medical occurrence in a patient or clinical investigation subject administered a pharmaceutical product and which does not necessarily have to have a causal relationship with this treatment.

An AE can therefore be any unfavorable and unintended sign (including an abnormal laboratory finding, for example), symptom, or disease temporally associated with the use of a medicinal product, whether or not considered related to the medicinal product. This includes any occurrence that is new in onset or aggravated in severity or frequency from the baseline condition.

An overdose, accidental or intentional, whether or not it is associated with an AE, or abuse, withdrawal, sensitivity or toxicity to an investigational product should be reported as an AE. If an overdose is associated with an AE, the overdose and adverse event should be reported as separate terms.

#### Serious Adverse Events (SAE)

A serious adverse event (SAE) is any untoward medical occurrence that at any dose:

- Results in death
- Is life-threatening (*the term "life-threatening" in the definition of "serious" refers to an event in which the patient was at risk of death at the time of the event; it does not refer to an event which hypothetically might have caused death if it were more severe*)
- Requires inpatient hospitalization or prolongation of existing hospitalization (hospitalization is defined as an inpatient admission, regardless of length of stay)
- Results in persistent or significant disability/incapacity
- Is a congenital anomaly/birth defect
- Is a medically significant event
- Is a suspected transmission of any infectious agent via a medicinal product.

Important medical events are defined as those occurrences that may not be immediately life threatening or result in death, hospitalization, or disability, but may jeopardize the subject or require medical or surgical intervention to prevent one of the other outcomes listed above. Medical and scientific judgment should be exercised in deciding whether expedited reporting is appropriated in other situations, such as important medical events that may not be immediately life-threatening or result in death or hospitalization but may jeopardize the patient or may require intervention to prevent one of the outcomes listed in the definition above.

The term "severe" is a measure of intensity, thus a severe AE is not necessarily serious. For example, "nausea of several hours" duration may be severe but may not be clinically serious.

#### Events not considered to be SAEs are hospitalizations for:

- A standard procedure for protocol therapy administration. However, hospitalization or prolonged hospitalization for a complication of therapy administration will be reported as an SAE.
- Routine treatment or monitoring of the studied indication not associated with any deterioration in condition.
- The administration of blood or platelet transfusion as routine treatment of studied indication. However, hospitalization or prolonged hospitalization for a complication of such transfusion remains a reportable SAE.

- A procedure for protocol/disease-related investigations (e.g., surgery, scans, endoscopy, sampling for laboratory tests, bone marrow sampling). However, hospitalization or prolonged hospitalization for a complication of such procedures remains a reportable SAE.
- Hospitalization or prolongation of hospitalization for technical, practical, or social reasons, in absence of an AE.
- A procedure that is planned (i.e., planned prior to starting of treatment on study); must be documented in the source document and the CRF. Hospitalization or prolonged hospitalization for a complication remains a reportable SAE.
- An elective treatment of a pre-existing condition unrelated to the studied indication.

If an AE is considered serious, both the AE page/screen of the CRF and the SAE Report Form on [www.drugvigilance.filinf.it](http://www.drugvigilance.filinf.it) must be completed.

For each SAE, the Investigator will provide information on severity, start and stop dates, relationship to IP, action taken regarding IP, and outcome.

### **Suspected Unexpected Serious Adverse Reaction (SUSAR)**

An unlisted adverse event, the nature or severity of which is not consistent with the applicable product information. For an investigational drug, the expectedness of an adverse event will be determined by whether or not it is listed in the Investigator's Brochure of experimental drug. For drugs with a marketing authorization, the expectedness of an adverse event will be determined by whether or not it is listed in the SmPC.

### **Severity**

The intensity of the toxicities, AE or SAE will be graded by the investigator according to the Common Terminology Criteria for Adverse Events (CTCAE) grading system version 5.0 in the toxicity categories that have recommended grading.

AEs not listed on this grading system will be graded according to the five-point system below:

Mild (grade 1)	Discomfort noticed but no disruption of normal daily activity
Moderate (grade 2)	Discomfort sufficient to reduce or affect normal daily activity
Severe (grade 3)	Incapacitating with inability to work or perform normal daily activity
Life-threatening (grade 4)	Substantial risk of dying at time of event
Death (grade 5)	Fatal

### **Causality**

The Investigator(s) must determine the relationship between the administration of study drug and the occurrence of an AE/SAE as Not Suspected or Suspected as defined below:

- **Not related.** An adverse event that is not related to the use of the investigational product.
- **Unlikely/Doubtful.** An AE for which an alternative explanation is more likely, e.g., concomitant drug(s), concomitant disease(s), or the relationship in time suggests that a causal relationship is unlikely.
- **Possible.** An AE that might be due to the use of the investigational product. An alternative explanation, e.g., concomitant drug(s), concomitant disease(s), is inconclusive. The relationship in time is reasonable; therefore, the causal relationship cannot be excluded.
- **Probable.** An AE that might be due to the use of the investigational product. The relationship in time is suggestive (e.g., confirmed by dechallenge). An alternative explanation is less likely, e.g., concomitant drug(s), concomitant disease(s).
- **Definite/Very likely.** An AE that is listed as a possible adverse event reaction, and cannot be reasonably explained by an alternative explanation, e.g., concomitant drug(s), concomitant disease(s). The relationship in time is very suggestive (e.g., it is confirmed by dechallenge and rechallenge).
- **Not assessable:** there is insufficient or incomplete evidence to make a clinical judgement of the causal relationship.

### 16.3. Serious Adverse Events reporting rules

All events that meet one or more criteria of seriousness (see above) occurred after the informed consent signature until the end of the study or early withdrawal for any cause, regardless of the relationship to the study treatment, will be reported as SAE.

After this time, SAE that occurs, during the follow-up period, if considered related to the study medication, will be reported.

Whenever possible, symptoms should be grouped as a single syndrome or diagnosis. The investigator should specify the date of onset, intensity, action taken regarding trial medication, corrective therapy given, outcome of all SAEs and his opinion as to whether the SAE can be related to the study drugs.

General SAE reporting rules:

- Any episode of any grade of toxicities, which meets one of the seriousness criteria, must be reported as “Serious Adverse Event” in the appropriate SAE form.
- Signs, symptoms and physical findings indicative of lymphoma or progression of lymphoma are not to be reported as “Serious Adverse Event”.
- “Alopecia” toxicity (any grade) will never be reported as “Serious Adverse Event”.

All AEs that occur from the first dose of study drug administration up to 30 days following the last dose of investigational product will be reported.

All SAEs that occur between the study informed consent signature and until the LPLV will be notified to the sponsor, using the FIL Serious Adverse Event reporting rules. The sponsor will evaluate any safety information that is spontaneously reported by an investigator beyond the time frame specified in the protocol.

All AEs and SAEs, regardless of seriousness, severity, or presumed relationship to study therapy, must be recorded in the CRF in accordance to the CTCAE criteria v 5.0. They must be recorded using medical terminology (MedDRA version 21.1).

Timely, accurate, and complete reporting and analysis of safety information from clinical studies are crucial for the protection of subjects, investigators, and the sponsor, and are mandated by regulatory agencies worldwide.

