### **Neutropenia**

Severe and life-threatening neutropenia, including febrile neutropenia, has been reported during treatment with obinutuzumab. Monitor patients with Grade 3 to 4 neutropenia frequently with regular laboratory tests until resolution. Anticipate, evaluate, and treat any symptoms or signs of

developing infection. Consider administration of granulocyte colony-stimulating factors (GCSF) in patients with Grade 3 or 4 neutropenia.

Consider dose delays in the case of Grade 3 or 4 neutropenia. Patients with severe and long lasting (> 1 week) neutropenia are strongly recommended to receive antimicrobial prophylaxis until resolution of neutropenia to Grade 1 or 2. Consider antiviral and antifungal prophylaxis.

In the event of febrile neutropenia or neutropenia with infection, hold obinutuzumab until febrile neutropenia or neutropenia with infection resolves.

- If Cycle 1 Day 8 is delayed long enough that the patient is approaching Day 15, then skip Day 8 and administer Day 15 as previously scheduled (if infection or fever has resolved)
- If Cycle 1 Day 15 is delayed long enough that the patient approaching Cycle 2, then skip Day 15 dosing and administer Cycle 2 Day 1 as scheduled (if infection or fever has resolved).

Neutropenia can also be of late onset (occurring more than 28 days after completion of treatment) and/or prolonged (lasting longer than 28 days).

For more details please refer to *Appendix F* or drug IB.

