#### **15.4. EOT phase**

at 4-6 weeks after last treatment administration

- Physical Examination;
- ECOG;
- Vital Signs;
- Hematology including Hemoglobin, Platelets, White blood cell count (WBC) with differential;
- Blood chemistry including creatinine, total bilirubin, LDH, AST, ALT, serum proteins with electrophoresis, immunoglobulin levels;
- Pregnancy test (if applicable);
- Electrocardiogram;
- LVEF by either bi-dimensional echocardiogram or cardiac scintigraphy (MUGA);
- Measurable lesion assessment on CT scan of neck, chest, abdomen and pelvis, to be performed with and without contrast (unless the subject already has had per-protocol assessments  $\leq 4$  weeks prior);
- FDG-PET scan (mandatory) unless the subject already has had per-protocol scan  $\leq 4$  weeks prior;
- Bone marrow biopsy only if positive at baseline;
- Molecular evaluation of BCL-2 rearrangement on marrow blood only if positive at baseline;
- Drug accountability
- AEs assessment
- Recording of concomitant medications.

Subjects lost to follow up should be recorded as such on the eCRF. All subjects who discontinue study treatment, including those who refuse to return for a final visit, should be contacted for a list of antineoplastic therapies received after discontinuation of study treatment.

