## 15.9. Schedule of assessments

	Screening	Treatment (Induction)						Restaging after 3 cycles, EOI, EOT, EW	Maintenance g	FU e	OS- FU
		Cycle 1			Cycle 2-6						
		-28 to D1	D1	D8	D15	D1	D8				
Informed consent	X										
Inclusion/Exclusion	X										
Medical History	X										
Height	X										
Weight	X	X	X	X	X						
Physical exam	X	X	X	X	X		X	X	X		
Pregnancy test	X	X	X	X	X		X	X	X		
Vital signs	X	X	X	X	X		X	X	X		
ECOG	X	X	X	X	X		X	X	X		
Hematology	X	X	X	X	X		X	X	X		
Chemistry	X	X	X	X	X		X	X	X		
Virology	X										
12-lead ECG	X						X h				
Tumor biopsy b	X										
CT of neck, chest, abdomen, pelvis	X						X f	X f	X f		
FDG-PET	X						X f	X f	X f		
LVEF measurement	X						X h				
BM biopsy	X						X a	X a	X a		
BCL-2 rearrangement	X						X ah				
B symptoms	X	X	X	X	X		X	X	X		
Idelalisib		BID									
Obinutuzumab		X	X	X	X			X g			
CMV monitoring c	X			X	X		X				

	Screening	Treatment (Induction)						Restaging after 3 cycles, EOI, EOT, EW	Maintenance g	FU e	OS- FU	
		Cycle 1			Cycle 2-6							
	-28 to D1	D1	D8	D15	D1	D8	D15					
PJP prophylaxis d		X	X	X	X	X	X	X				
Survival follow up contact											X	
Concomitant medications	Recorded from screening through 30 days after the last dose of treatment.											
Adverse event reporting		Recorded from first dose of study drug through 30 days after the last dose of treatment.										
Serious adverse event	Reported from signing of the informed consent from through last patient last visit											

a only if positive at baseline/previous assessment;

b Histological centralized review is compulsory for treatment start, but the local pathology report is sufficient for patient enrollment;

c Every two weeks starting from C1D1;

d All patients will receive prophylaxis for PJP during idelalisib treatment and for 2 to 6 months after stopping treatment; patients have to be monitored for respiratory signs and symptoms;

e Every 6 months for 2 years only for CR, PR or SD patients at the end of treatment until PD, unacceptable toxicity or a new anti-lymphoma therapy;

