#### Adverse Events

All adverse events will be listed. The focus of AE summarization will be on treatment-emergent adverse events. A treatment-emergent adverse event is defined as an AE that occurs or worsens in the period from the first dose of study drugs to 30 days after the last dose of study drug. AEs that occur before the first dose of study treatment or >30 days after the subject has been discontinued from study treatment will be included in data listings.

AEs will be classified using MedDRA version 21.1 with descriptions by System Organ Class, High-Level Group Term, High-Level Term, Preferred Term, and Lower-Level Term. The severity of adverse events will be graded by the investigator according to the [CTCAE, Version 5.0](#), whenever possible. If a CTCAE criterion does not exist for a specific type of adverse event, the grade corresponding to the appropriate adjective will be used by the investigator to describe the maximum intensity of the adverse event: Grade 1 (mild), Grade 2 (moderate), Grade 3 (severe), Grade 4 (life threatening), or Grade 5 (fatal). The relationship of the AE to the study drug will be categorized as related or unrelated.

A subject who reports multiple treatment emergent AEs within the same Preferred Term (or System Organ Class) is counted only once for that Preferred Term (or System Organ Class) using the worst severity grade.

AE descriptions will be presented by decreasing frequency for a given System Organ Class and Preferred Term.

Separate listings and summaries will be prepared for the following types of treatment-emergent adverse events:

- Study-drug-related (idelalisib or obinutuzumab) adverse events
- AEs that are Grade  $\geq 3$  in severity
- AEs leading to study drug interruption and/or dose modification
- AEs leading to study drug (idelalisib or obinutuzumab) discontinuation
- SAE (with categorization of the primary reason that the adverse event is considered serious, e.g., death, hospitalization, etc)

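### Non-serious AEs are collected only to day 30 after the last dose, so non-serious late-onset neutropenia starting later is not collected as an AE, even when the end-of-treatment blood count shows it

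*Combined protocol and SAP*

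**What the plan says.** **AE collection.** Section 16.3 has AEs reported from the first dose "up to 30 days following the last dose of investigational product will be reported". The grid in section 15.9 agrees: "Recorded from first dose of study drug through 30 days after the last dose of treatment". Section 17.3 applies the same 30-day limit to treatment-emergent AEs, on which the summaries concentrate. It adds that AEs arising ">30 days after the subject has been discontinued from study treatment will be included in data listings".

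**SAE collection.** This runs longer. Section 16.3 states: "All SAEs that occur between the study informed consent signature and until the LPLV will be notified to the sponsor". The grid in section 15.9 says the same: "Reported from signing of the informed consent from through last patient last visit". Section 16.3 also holds a second rule, under which only SAEs considered related are reported during follow-up.

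**The toxicity.** In the obinutuzumab part of section 13.12: "Neutropenia can also be of late onset (occurring more than 28 days after completion of treatment").

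**The visits.** Section 15.4 sets the EOT visit "at 4-6 weeks after last treatment administration" and lists both hematology and an AE assessment. The six-monthly follow-up visits in section 15.6 include laboratory tests but list no AE assessment. Survival follow-up (section 15.7) can be done by telephone and has no laboratory tests.

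**The endpoint.** Section 9.4 makes the incidence, type and grade of AEs and SAEs part of a secondary endpoint and sets no time limit. The synopsis refers to AEs during treatment and shortly after it.

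**The concern.** The protocol describes a toxicity whose onset begins almost exactly where AE collection ends. It then schedules a blood count and an AE assessment in a window that lies mostly beyond that end. A site that finds a new Grade 3-4 neutrophil count at the EOT visit on day 35, in a patient who is otherwise well, gets different signals from different sections: 15.4 prompts an AE assessment, 16.3 and 15.9 say that collection has closed, and 17.3 speaks of listing late AEs.

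What is at stake is how completely a secondary safety endpoint is ascertained. The trial has a single arm, so no control group shares the same under-ascertainment. The primary endpoint is unaffected, and so is the toxicity stopping rule in section 17.2, which covers non-hematological toxicity.

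**Working it through.** The plan states no figure to reproduce; the check is calendar arithmetic. Days are counted from the last dose of either study drug (day 0).

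**1. Late-onset period against AE collection.** Late onset is more than 28 days after treatment (13.12), so day 29 onward. Collection ends on day 30 (16.3, 15.9). Overlap: 30 − 29 + 1 = 2 days.

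**2. EOT visit against AE collection.** Four to six weeks is 4 × 7 = 28 to 6 × 7 = 42 days, which gives 42 − 28 + 1 = 15 possible visit days. Days 28-30 (3 days) fall on or before the cut-off; days 31-42 (12 days) fall after it. This shows when a visit may be held. It does not count lost events, because a visit on day 35 can still record an event that began on day 25.

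**3. One case traced through the text.** A Grade 3-4 neutropenia starts on day 35 and is found at the EOT visit that day.

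| Rule | If non-serious | If serious |
|---|---|---|
| 15.4 visit | Blood count and AE assessment are done | Same |
| 16.3 and 15.9 AE window | Not collected | Not collected under the AE rule |
| 16.3 and 15.9 SAE window | Not applicable | Reported |
| 17.3 treatment-emergent tables | Not counted | Not counted |
| 17.3 listing | No collection rule supplies it | Supplied by the SAE record |

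Only the non-serious column is a gap.

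**4. The anchor matters.** In cycle 6 obinutuzumab is given on day 1, while idelalisib continues daily through day 28 (13.3), that is 27 days later. For a patient who completes induction on both drugs and has no maintenance, the window reaches 27 + 30 = 57 days after the last obinutuzumab dose. If the 28 days in 13.12 are counted from obinutuzumab, days 29-57 (29 days) are observable in that patient, not 2. For a patient in maintenance the last dose is obinutuzumab, so the two-day overlap applies after the last maintenance dose and everything before that dose is inside the window. Within 17.3 the anchors also differ: last dose for treatment-emergent AEs, discontinuation for the listing.

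**5. Illustration of scale.** The documents give no onset distribution. Assume only for illustration that non-serious onsets are spread evenly from day 29 to day T, counted from the last dose of either drug.

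| T | Inside the present window | Inside a window to day 42 |
|---|---|---|
| 42 | 2/14 = 14% | 14/14 = 100% |
| 90 | 2/62 = 3.2% | 14/62 = 22.6% |
| 180 | 2/152 = 1.3% | 14/152 = 9.2% |

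The shares depend almost wholly on T, so they are not estimates. They do show that a window to day 42 captures what the EOT visit can already see, and not all late-onset cases.

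**The case against.** The best defence is that a fixed 30-day window satisfies the synopsis, and that the cases that matter most are captured elsewhere. Much of this stands.

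- **Serious cases are kept.** SAEs belong to the endpoint in 9.4 and are reported to the last patient's last visit. Even the narrower rule in 16.3 keeps related SAEs. Appendix F lists 290 serious neutropenia and 320 febrile neutropenia reactions for obinutuzumab, so neutropenia often qualifies. A reader might infer that the toxicity as a whole falls outside the safety endpoint; it does not.
- **The listing in 17.3 has a source.** It can be filled by SAEs, which are also entered on the AE page of the CRF (16.2). It is not proof that late non-serious AEs were meant to be collected.
- **A visit after day 30 loses no earlier event.** Reading 12 of 15 visit days (80%) as a loss is therefore wrong.
- **Much lies inside the window.** Neutropenia arising during maintenance is collected. Events that begin inside the window are followed to resolution (16.5), so prolonged neutropenia is kept.
- **The near-zero reading is unsupported.** It is tempting to say that the plan would report almost no late-onset neutropenia by construction. Serious cases, the anchor in step 4 and the missing onset distribution all rule that out. Nor can all 43 patients be called affected: the gap concerns only those with a non-serious onset after day 30, and the early-withdrawal visit in 15.8 states no 4-6 week interval.

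What the defence does not answer is the non-serious case. Grade 3-4 neutropenia that meets no seriousness criterion is not an SAE, and neutropenia is not among the AEs of special interest in 16.3. The sponsor's undertaking there to evaluate late spontaneous reports is not systematic collection.

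**Conclusion.** The point holds in a limited form. Non-serious neutropenia, including Grade 3-4, with onset after day 30 from the last dose of either drug is not collected as an AE, although the protocol names late onset as possible and a planned visit may measure it on days 31-42. This is an inexpensive improvement to a secondary safety endpoint; it does not threaten the trial's main conclusion.

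Its size can be given only as a period: 2 days of the late-onset period are covered, and 12 further days fall within the EOT visit range but outside collection. Both counts assume that day 0 is the last dose of either drug. The number of events missed cannot be derived from the documents.

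**What to change.** 1. In sections 16.3, 15.9 and 17.3, use one AE collection window with one anchor, the last dose of either study drug, running to a fixed day 42. A fixed day covers the EOT visit and gives each patient the same nominal window, which ending at the visit itself would not.
2. Keep the 30-day treatment-emergent tables as they are, so that they stay comparable, and report AEs with onset on days 31-42 separately.
3. Record as late-onset AEs any Grade 3 or higher neutropenia or infection noted at follow-up visits already scheduled. State that six-monthly laboratory tests, and survival follow-up without laboratory tests, make this ascertainment incomplete.
4. Reconcile the two SAE rules in section 16.3: all SAEs to the last patient's last visit, or only related SAEs during follow-up.

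The cost is amendment wording, a few extra eCRF entries and slightly higher reported AE counts. No new visit or sample is needed.
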